8.5.5. Secondary Objective #3

Evaluate the change in the time to receiving an indicated IPG device for SND subjects before and after intervention.

This document is electronically controlled. Printed copies are considered uncontrolled.

Confidential

8.5.5.1. Analysis Methods

A. Statistical Methodology

A log-rank test of two Kaplan-Meier curves will determine if there is a significant difference in the time to implant before and after intervention, within the South Asia geography. Descriptive statistics will be used to characterize the number of visits that occur between the diagnosis and implant and further will examine number of visits separated by Phase, type of enrolling physician, and possibly other baseline characteristics.

B. Determination of Patients/Data for Analysis

The subjects to include in the analysis of Objective 3 in Section **Error! Reference source not found.** are the same as specified in section **Error! Reference source not found.** for Primary Objective 2.

C. Additional Analyses

In addition to the time to event analysis, a Cox model will test covariates of interest that may include gender, age, HF, NYHA class and ejection fraction and the impact on time to implant. A characterization will also be provided that describes covariates of interest and whether or not the implant was CRT instead of an IPG

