5.7 Study Exit

Subjects may be exited from the study for any of the following situations, including but not limited to:

- Subject does not meet an indication for pacing therapy
- Subject meets an indication for pacing but not a SND indication for pacing therapy
- Subject has met a SND indication for pacing therapy and did not receive a market released pacemaker from the Medtronic family of devices
- Subject has met a SND indication for pacing therapy but will not be receiving pacing therapy
- Subject has completed the final scheduled follow-up visit.

- Geography/country completion of Phase I follow-up
- Study Closure
- Subject lost to follow-up
- Subject death
- Subject did not meet inclusion/exclusion criteria
- Subject chooses to withdraw (e.g., consent withdrawal, relocation to another geographic location)
- Investigator deems withdrawal necessary (e.g., medically justified, failure of subject to maintain adequate study compliance)

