For Secondary Objectives 2 and 3 above, the following statistical analysis is proposed. A stratified log-rank test of two Kaplan-Meier curves will determine if there is a significant difference in the time to endpoint before and after intervention. The stratification will occur by geography/country and also by site. Stratified Cox models may also be fit to examine independent variables of interest that may affect SND diagnosis, such as gender and age. Descriptive statistics will be used to characterize the number of visits that occur before an SND diagnosis and between the diagnosis and implant and further will examine number of visits separated by Phase, geography/country, type of enrolling physician, and possibly other baseline characteristics.

B. Determination of Patients/Data for Analysis

The subjects to include in the analysis of secondary objectives 2 and 3 are the same as specified for primary objectives 1 and 2 respectively.

Secondary Objective #4

Evaluate the Caregiver burden between pre-implant and 6 months post-implant

Endpoint Definition

Compare the difference in caregiver burden from pre-implant to 6 months post-implant

Analysis Methods**A. Statistical Methodology**

Descriptive statistics will be used to summarize the difference in caregiver burden between pre-implant and 6 months post-implant.

B. Determination of Patients/Data for Analysis

Subjects in Phase II who opt to receive an indicated therapy and are implanted with a market released pacemaker from the Medtronic family of devices will be followed from implant to 6 months post-implant. The primary caregiver of these subjects will be asked to complete a questionnaire that assesses caregiver burden at the time of implant and 6 months post-implant.

Secondary Objective #5

Evaluate change in Quality of Life (QOL) and functional status between pre-implant and 6 months post-implant.

Endpoint Definition

Compare the difference in QOL and functional status between pre-implant and 6 months post-implant.

Analysis Methods**A. Statistical Methodology**

Descriptive statistics will be used to summarize the difference in QOL and functional status between pre-implant and 6 months post-implant.

B. Determination of Patients/Data for Analysis

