4.2.2. Secondary Objective #2

Evaluate the change in the time to diagnosis of SND before and after intervention.

4.2.2.1. *Endpoint Definition*

Time to diagnosis in days (date of diagnosis – date of enrollment); number of visits to diagnosis

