4.2.3. Secondary Objective #3

Evaluate the change in the time to receiving an indicated IPG device for SND subjects before and after intervention.

4.2.3.1. *Endpoint Definition*

Time to treatment in days (date of implant – date of diagnosis); number of visits to treatment

This document is electronically controlled. Printed copies are considered uncontrolled.

Confidential

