4.2.5.1. Endpoint Definition

Compare the difference in QOL and functional status between pre-implant and 6 months post-implant. The composite physical and mental scores from Version 2 of the SF-12 Health Survey will be used to assess QOL.

[REDACTED]

[REDACTED] [REDACTED]

[REDACTED]

[REDACTED]

[REDACTED]

[REDACTED] [REDACTED]

[REDACTED]

This document is electronically controlled. Printed copies are considered uncontrolled.

Confidential

[REDACTED]

[REDACTED]

[REDACTED]

[REDACTED]

[REDACTED]

[REDACTED]

5. Investigation Plan

Study Design Overview

The study may be conducted in countries located in Central and Eastern Europe (CEE), Greater China, India, Latin America, Asia, and Middle East and Africa (MEA). Countries from other geographies may be added in the future. The distribution of centers will be approximately 10 per geography or country and is determined by local evidence needs.

Approximately 1,650 subjects per geography/country, or up to 14,850 subjects worldwide, will be enrolled in the study. An enrollment target of 6 subjects per center per month is desired to make center-specific outcomes more meaningful and reliable in measuring changes in diagnostic rates and patient acceptance of indicated therapy. Centers that enroll faster than others will be allowed to enroll until 20% of the sample size for the geography/country has been reached for a maximum of 330 subjects per site - 110 maximum in Phase I and 220 maximum in Phase II.

All study subjects will be followed until the study exit criteria are met or until official study closure. Study closure is defined as closure of a clinical study that occurs when Medtronic and/or regulatory requirements have been satisfied per the Clinical Investigation Plan and/or by a decision by Medtronic or regulatory authority, whichever occurs first. The expected study duration per geography/country, from first enrollment to last follow-up, is approximately 4.5 years per geography/country.

Subjects will have successfully completed the study if one of the following criteria has been met:

1. Subject does not meet a class I or class II SND indication for pacing therapy
2. Subject meets an indication for pacing but not an SND indication for pacing therapy
3. Subject has met an SND indication for pacing therapy and did not receive a market released pacemaker from the Medtronic family of devices
4. Subject has met an SND indication for pacing therapy but will not be receiving pacing therapy

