8.5.2.1. Analysis Methods

A. Statistical Methodology

To compare the proportion of subjects that receive indicated therapy pre-intervention (Phase I) to the proportion post-intervention (Phase II), a Fisher's Exact test will determine statistical significance. A Fisher's exact test is recommended for smaller sample sizes. The proportion of subjects diagnosed will be evaluated at multiple time points because the time from diagnosis to implant is expected to vary by geography. Shorter time intervals will be used to evaluate the proportion of implants than for the proportion of diagnosis because time from diagnosis to implant is typically shorter than the time from enrollment to SND diagnosis. Thus, times are pre-specified starting at 3 months and any additional 3-month interval thereafter for which there is sufficient follow-up data available to compare study phases. Proportions calculated at all available time points will be reported. Additionally, a Poisson regression will compare the average number of subjects with an implant where the subject time in study beginning at the time of SND diagnosis is treated as an offset in the model. The above described tests will be performed only for the South Asia geography as described in Section 6. Further, similar tests will compare the differences in the types of therapy received in Phase I and Phase II. For example, a Fisher's exact test will compare the frequency of dual chamber device use pre- and post-intervention.

This document is electronically controlled. Printed copies are considered uncontrolled.

Confidential

B. Determination of Patients/Data for Analysis

Subjects that meet inclusion criteria and obtain an SND diagnosis shall be included in this analysis. The proportion estimates will be calculated based on information from fixed time points at 3 months of follow-up, 6 months of follow-up, and any additional 3-month interval thereafter for which there is sufficient follow-up data available to compare study phases. The number of subjects that obtain an IPG by pre-specified time point $t = 3, 6, \text{ etc.}$, will be included in the numerator and the number of subjects with an SND diagnosis will be included in the denominator.

C. Additional Analyses

- In addition to the overall diagnosis and treatment rates between Phase I and Phase II, various descriptive summaries of the subjects will be explored by geography, including the following:

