8.5.4.1. Analysis Methods

A. Statistical Methodology

A log-rank test of two Kaplan-Meier curves will determine if there is a significant difference in the time to diagnosis before and after intervention, within the South Asia geography. [REDACTED]

[REDACTED]

[REDACTED]

[REDACTED]

Cox models may also be fit to examine independent variables of interest that may affect SND diagnosis, such as gender and age. Descriptive statistics will be used to characterize the number of visits that occur before an SND diagnosis and further will examine number of visits separated by Phase, type of enrolling physician, and possibly other baseline characteristics. [REDACTED]

This document is electronically controlled. Printed copies are considered uncontrolled.

Confidential

B. Determination of Patients/Data for Analysis

The subjects to include in the analysis of Secondary Objective 2 in Section **Error! Reference source not found.** are the same as specified in Section **Error! Reference source not found.** for Primary Objective 1.

C. Additional Analyses

In addition to the time to event analysis, various additional analyses of the subjects will be explored, including a description of diagnostic tests performed when there is a delay in a patient's diagnosis. The endpoint is time to diagnosis and variables of interest are the different types of diagnostic tests. A table will be created with a format as follows:

Tests performed	SND dx 0-6 months	SND dx 6-12 months	SND dx 12-18 months
ECG	Number of tests, number of subjects		
Tilt table			
ILR			
Holter			
Average number of tests performed			

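### The Kaplan-Meier and log-rank plan for time to diagnosis and time to implant has no visible rule for subjects who exit because the event will not happen

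*SAP*

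**What the plan says.** **Tests.** SAP 8.5.4.1 (Secondary Objective #2): "A log-rank test of two Kaplan-Meier curves will determine if there is a significant difference in the time to diagnosis". SAP 8.5.5.1 (Secondary Objective #3): "A log-rank test of two Kaplan-Meier curves will determine if there is a significant difference in the time to implant". Protocol 11.2 plans a stratified form for both: "A stratified log-rank test of two Kaplan-Meier curves will determine if there is a significant difference in the time to endpoint".

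**Endpoints.** SAP 4.2.2 and 4.2.3 define the times only for subjects who have the event: "Time to diagnosis in days (date of diagnosis – date of enrollment" and "Time to treatment in days (date of implant – date of diagnosis", each with the closing bracket omitted here. Neither says what time is given to a subject who never has it.

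**Exits.** Protocol 5.7 permits exit in several situations, among them "Subject does not meet an indication for pacing therapy", an indication for pacing that is not SND, and an SND indication without pacing to follow. SAP Section 5 lists the same kinds of exit as successful completion of the study, including "Subject has met an SND indication for pacing therapy but will not be receiving pacing therapy". Protocol 5.9 adds that nothing is collected after withdrawal.

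**Populations.** Time to diagnosis uses all enrolled subjects. Time to implant uses the population of Primary Objective #2: "Subjects that meet inclusion criteria and obtain an SND diagnosis shall be included in this analysis".

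**Not stated.** No visible text gives a censoring rule or names a competing event. Blocks are redacted after the log-rank sentence in SAP 8.5.4.1. None is shown in SAP 8.5.5.1.

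**The concern.** Kaplan-Meier and log-rank methods rest on independent censoring: a subject censored at time t should have the same later chance of the event as those still followed. A subject who leaves with a final non-SND diagnosis, or after a decision against pacing, has little or no such chance within the study. These are outcomes in their own right, and the SAP itself counts them as completion.

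Two things are at stake. First, if such exits are censored, one minus Kaplan-Meier is too high as an estimate of the proportion diagnosed or implanted. Second, the log-rank test then responds to how fast non-takers leave as well as to how many subjects have the event and when. Protocol 4.3 says the toolkit may include diagnostic algorithms and tools that educate patients on therapy options. Faster rule-out or faster refusal in Phase II is therefore plausible, though the documents give no evidence on it.

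The two exit types bear on different objectives. Rule-out matters for time to diagnosis. A decision against pacing matters for time to implant, whose population already has an SND diagnosis.

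**Working it through.** The plan gives no power, event count or sample size for Secondary Objectives #2 and #3, so there is no figure of its own to reproduce.

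**Inputs from the documents.** SAP 8.5.1.2: 500 and 1000 subjects, 20% diagnosed at six months. SAP 8.5.2.2: 100 and 200 SND subjects, 10% implanted at three months after diagnosis, 26% as the alternative, type I error 0.05 (taken as two-sided).

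**Assumed inputs.** All exit shares, exit times and event-time distributions.

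**Step 1: inflation of the curve.** Let F be the true proportion with the event by time t and q the proportion that has exited without it. With constant hazards, and exits censored:

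1 − KM(t) = 1 − (1 − F − q)^(F/(F + q))

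For F = 0.10 and q = 0.40: 1 − 0.50^0.20 = 12.9%.

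| True proportion F | q = 20% | q = 40% | q = 60% | q = 70% |
|---|---|---|---|---|
| Implant, 10% at 3 months | 11.2% | 12.9% | 15.8% | 18.2% |
| Implant, 26% at 3 months | 29.4% | 34.6% | 44.8% | 58.2% |
| Diagnosis, 20% at 6 months | 22.5% | 26.3% | 33.1% | 40.1% |

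The primary objectives (SAP 8.5.1.1 and 8.5.2.1) divide by all enrolled or all SND-diagnosed subjects. Before any other loss to follow-up they would estimate F itself, so the two analyses would report different percentages at the same time point.

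**Step 2: log-rank for time to implant, no true phase difference.** Simulated with 100 and 200 subjects, eventual uptake 10% in both phases, exponential implant time with mean 1.5 months, exponential exit time for decliners, and a six-month window.

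| Mean exit, Phase I vs Phase II (months) | Rejection, censored at exit |
|---|---|
| equal | about 5% |
| 2 vs 1.5 | 8% |
| 2 vs 1 | 34% |
| 3 vs 1 | 57% |

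With decliners kept at risk to six months, rejection is about 5% throughout. If mean implant time is 0.5 month instead of 1.5, the 2 versus 1 case gives only 9%.

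**Step 3: log-rank for time to diagnosis, no true phase difference.** Simulated with 500 and 1000 subjects, 20% diagnosed in both phases, median time to diagnosis 2 months, and administrative follow-up of 6 to 18 months (Phase I) and 6 to 24 months (Phase II). Rejection is 5.1% if median rule-out is 3 months in both phases, 57% if it falls from 3 to 2, and 63% if it falls from 6 to 3. If it lengthens from 2 to 3 the test rejects 50% of the time, against Phase II. Keeping ruled-out subjects at risk gives 4.4% to 5.6%.

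**Step 4: power.** With a real 10% versus 26% difference in implants and equal mean exit of 1 month, log-rank power is about 0.76 with exits censored and 0.92 with decliners kept at risk.

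Monte Carlo error is about 1 point near 5% and 2 points near 50%.

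**The case against.** **The plan never says that these subjects are censored at exit.** True. That is the default of the named method, not stated text, and a rule for time to diagnosis could lie under the redactions in SAP 8.5.4.1. A reader might infer that the plan prescribes ordinary censoring. The documents support only that no rule is visible. The redaction argument does not help for time to implant.

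**The later risk is not zero by definition.** Also true. Exit is permissive, a decision against pacing could be reversed, and one exit category covers subjects who did not receive a sponsor device, which might include an implant of another make. Lack of a pacing indication (an exit reason) is also not the same item as lack of an SND diagnosis, which SAP 4.1.1.1 takes from the Diagnosis Form. This softens the point but does not restore independent censoring.

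**The log-rank test is still valid for cause-specific hazards.** Correct, and whether a result is false depends on the estimand. But the SAP does not state that estimand, and even then one minus Kaplan-Meier is not a proportion diagnosed or implanted.

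**The primary objectives already handle absolute risk.** They do, at fixed times. That limits the damage, but it leaves the plan with two sets of percentages that would not agree.

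**The size depends on chosen exit times.** It does. In the 2 versus 1 month case of Step 2, one minus Kaplan-Meier at six months is 23% versus 63% against a true 9.8% in both phases. A reader might take that gap as the headline, but only about 4.7 of 100 and 0.8 of 200 subjects are then still at risk. At three months the curves read 15% and 27% against a true 8.6%.

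**Conclusion.** The concern holds as a gap in the specification with a misleading default. If rule-out and decline exits are censored, the curves overstate the proportion diagnosed or implanted even when exit patterns are the same in both phases. The excess is modest when few exit (10% reads as 11.2% with 20% exited) and large when most do (18.2% with 70% exited).

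A spurious phase difference is conditional. It needs exit speed to differ by phase, and it ranges from 8% rejection for a mild shift to 57% for a large one in the implant setting. With equal exit the test keeps about 5%. A reader might conclude that the planned log-rank test will produce a false result. The documents do not support that, because they contain no exit timings and no evidence that the toolkit changes them.

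Only secondary objectives are affected. SAP 4.1 calls the study exploratory and sets no hypotheses for the primary objectives, but Protocol 4.1 lists these as key secondary objectives with hypotheses to be tested, so the point should be acted on. Confidence is medium, because the handling of exits is not visible and the sizes rest on assumed timings.

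**What to change.** In SAP 8.5.4.1 and 8.5.5.1:

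- State how each exit reason enters the analysis. Treat as competing events a final non-SND diagnosis (Secondary Objective #2), a final decision against pacing (Secondary Objective #3), and death (both).
- Report cumulative incidence by phase with Gray's test, keeping subjects with a competing event in the risk set to the administrative cut-off for their phase.
- Censor only for loss to follow-up, withdrawal and study closure, including completion of Phase I follow-up.
- Say whether an implant of another make counts as an event.
- Tabulate exit reason and time to exit by phase.
- If the log-rank test is kept, label it a comparison of cause-specific hazards and do not read one minus Kaplan-Meier as the proportion diagnosed or implanted.

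The cost is SAP wording and a different procedure call. Protocol Table 1 already collects final diagnosis, treatment decision, death and reason for exit, so no new data item is needed.

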8.5.6. Secondary Objective #4

Evaluate the Caregiver burden between pre-implant and 6 months post-implant.

This document is electronically controlled. Printed copies are considered uncontrolled.

Confidential

8.5.6.1. Analysis Methods

A. Statistical Methodology

Descriptive statistics will be used to summarize the difference in caregiver burden between pre-implant and 6 months post-implant. The Zarit Burden Interview is a 22 question survey, with each question scored on a scale of 0 to 4. The total score is the sum of all 22 question responses. A t-statistic will test the difference between the total score of the survey between pre-implant (zarit0) and 6 month post-implant (zarit6). [REDACTED]

[REDACTED]

The primary analysis will deal with missing values by scaling the total score of the non-missing responses. If at least 50% of the survey has been completed, the total score of the non-missing responses will be multiplied by (22/number of non-missing responses). If less than half of the questions were answered, the survey will not be included in the analysis. Missing values will be dealt with using a multiple imputation procedure as a sensitivity analysis.

B. Determination of Patients/Data for Analysis

Subjects in Phase II who opt to receive an indicated therapy and are implanted with a market released pacemaker from the Medtronic family of devices will be followed from implant to 6 months post-implant. The primary caregiver of these subjects will be asked to complete a questionnaire that assesses caregiver burden at the time of implant and 6 months post-implant.

8.5.7. Secondary Objective #5

Evaluate change in quality of life (QOL) and functional status between pre-implant and 6 months post-implant.

8.5.7.1. Analysis Methods

A. Statistical Methodology

Descriptive statistics will be used to summarize the difference in QOL and functional status between pre-implant and 6 months post-implant. The SF-12 survey results will be compared at implant and at six

This document is electronically controlled. Printed copies are considered uncontrolled.

Confidential

months of follow-up. A t-statistic will test the difference in the survey scores between the two time points. The eight sub-domains of the SF-12 may also be tested.

Composite scores are calculated by first appropriately summarizing eight scales from the individual SF-12 questions.

- Physical Functioning (PF) - Items 2a+2b
- Role Physical (RF) - Items 3a+3b
- Bodily Pain (BP) - Item 5
- General Health (GH) - Item 1
- Vitality (VT) - Item 6b
- Social Functioning (SF) - Item 7
- Role Emotional (RE) - Items 4a+4b
- Mental Health (MH) - Items 6a+6b

If at least half of the items within any scale have been completed, any missing values within those scales can be imputed as the average response of all remaining questions from that scale for that respondent within the survey taken on that visit (Chapter 6 of SF-36 Health Survey Manual and Interpretation Guide).

Once the eight scales have been summarized, they are each normalized by their 1998 general US population means and standard deviations, and a linear combination of the scales are combined to calculate the composite physical and mental scores (Chapter 8 of How to Score Version 2 of the SF-12 Health Survey).

B. Determination of Patients/Data for Analysis

Subjects in Phase II who opt to receive an indicated therapy and are implanted with a market released pacemaker from the Medtronic Family of devices will be followed from implant to 6 months post-implant. These subjects will be asked to complete a questionnaire that assesses their QOL at the time of implant and 6 months post-implant.

This document is electronically controlled. Printed copies are considered uncontrolled.

Confidential

[REDACTED]

This document is electronically controlled. Printed copies are considered uncontrolled.

Confidential

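### SAP 8.5.7.1 assigns SF-12 item 6b to both Vitality and Mental Health, leaving one of the 12 items unscored; followed as written, it mis-scores at least one scale and the QOL composites

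*SAP*

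**What the plan says.** SAP 4.2.5.1 names the composite physical and mental scores of SF-12 Version 2 as the QOL measure for Secondary Objective #5. SAP 8.5.7.1 sets out how they are obtained. The first step is "Composite scores are calculated by first appropriately summarizing eight scales from the individual SF-12 questions", followed by a list of the items in each scale. Two entries in that list share an item: "Vitality (VT) - Item 6b" and "Mental Health (MH) - Items 6a+6b".

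A missing-item rule follows, which applies "If at least half of the items within any scale have been completed" and is referenced to the SF-36 manual. The scales are then normalised to 1998 US population values, and "a linear combination of the scales are combined to calculate the composite physical and mental scores". That last step is referenced to "Chapter 8 of How to Score Version 2 of the SF-12 Health Survey".

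On inference the section says "A t-statistic will test the difference in the survey scores between the two time points", and adds "The eight sub-domains of the SF-12 may also be tested".

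**The concern.** The item list is the only item-to-scale map visible in either document, and the SAP presents it as the first step of scoring. If each item belongs to one scale, an item that appears in two scales is wrong in at least one of them, and some other item has been dropped.

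The error would not stay inside one scale. The composites are linear combinations of all eight scales, so a wrong Vitality or Mental Health score carries into them. The sub-domain tests could also report the wrong scale directly. Improved QOL is one of the claims that Protocol 1.1 expects the study to support.

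The missing-item rule inherits the fault, because it works scale by scale and cannot act on an item that no scale contains.

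**Working it through.** **Inputs.** The item list is from SAP 8.5.7.1. The total of 12 items is an assumption: it is read from the instrument's name and agrees with the number of slots in the list, but the questionnaire is not reproduced. There is no planned figure to reproduce here; the check is a count.

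| Scale | Items listed | Slots |
|---|---|---|
| Physical Functioning | 2a, 2b | 2 |
| Role Physical | 3a, 3b | 2 |
| Bodily Pain | 5 | 1 |
| General Health | 1 | 1 |
| Vitality | 6b | 1 |
| Social Functioning | 7 | 1 |
| Role Emotional | 4a, 4b | 2 |
| Mental Health | 6a, 6b | 2 |

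**Count.**
- Slots: 2 + 2 + 1 + 1 + 1 + 1 + 2 + 2 = 12.
- Distinct items: 1, 2a, 2b, 3a, 3b, 4a, 4b, 5, 6a, 6b, 7 = 11.
- Cross-check: 10 items used once + 6b used twice = 12 slots.
- Unscored items: 12 - 11 = 1.
- Question 6 has 3 slots but only 2 distinct items; 6b fills 2 of the 3.

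**Which line is wrong.** Call the unlisted item x. Replacing 6b by x in Vitality gives 12 slots and 12 distinct items. Replacing it in Mental Health gives the same. The count therefore proves that a fault exists but does not locate it. The lettering suggests that x is a third part of question 6, but the documents do not confirm this.

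**Effect on a scale.** Use mean-item scoring, with 6b and x coded in the same direction. Let d = (mean pre/post change in 6b) - (mean pre/post change in x).
- Mental Health line wrong: (6a + 6b)/2 - (6a + x)/2 = 0.5 x (6b - x), so the change is off by 0.5 x d.
- Vitality line wrong: 6b - x = 1 x (6b - x), so the change is off by 1 x d.

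**Effect on the composites.** If a scale S is normalised as (S - m)/s, its pre/post change is (S at 6 months - S at implant)/s. The norm mean m cancels, so a constant offset does no harm to the change score. The error in the change does not cancel. It enters each composite as (that scale's weight) x (error in change)/s. The SAP gives neither the weights nor s.

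**Effect on missing items.** As listed, a missing 6b leaves Vitality with 0 of 1 items, so it cannot be scored. Mental Health keeps 1 of 2 items, which meets the half-scale rule, so it is imputed from 6a alone. A missing x has no effect, because x is in no scale.

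**The case against.** The strongest reply is that this is a typing slip with no consequence. The composites cannot be programmed from the SAP alone, because the norm means, standard deviations and weights are only in the cited manual. Anyone who opens the manual for those will probably take the item map from it too. SAP section 9 also requires level II or better validation for secondary objectives. This makes the harmful scenario less likely, and the results are unharmed if the manual is followed. But the manual is cited for normalisation and composites, not for the list. The validation level is not defined in the visible text, and a check made against the SAP list would reproduce the fault.

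A second reply concerns the text itself. The point turns on one character, the public file was read from PDF, and pages nearby are redacted. A misread letter, or correct scoring code under the redaction, cannot be excluded. The list otherwise reads cleanly, and the sponsor can settle this at once from the source file. The label RF beside Role Physical, in a list that uses RE for Role Emotional, may mean that the list was not proofread, although it could also be a reading error.

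A third reply is that the 0.5 factor depends on mean-item scoring, whereas the SAP writes the items as a sum. That is right: on the raw sum, (6a + 6b) - (6a + x) is off by 1 x d. The choice of scaling changes the multiplier, not the existence of the error.

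Finally, Protocol 11.2 plans only descriptive statistics for this objective. That lowers the stakes, but the SAP adds a test, and the summaries themselves would be wrong if the list were used.

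**Conclusion.** The list is wrong as written. One of 12 items is unscored, one is scored twice, and 2 of 8 scales are involved, at least 1 of them incorrectly. This rests on the instrument having 12 items with each in one scale, and on the public text matching the signed SAP.

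Whether results are affected depends on whether scoring follows the list or the manual. If it follows the list, the error in mean-item change is 0.5 x d (Mental Health) or 1 x d (Vitality). It then reaches the composites through weights that the documents do not give. The size cannot be determined, and it is zero if 6b and the displaced item change equally.

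The reach is narrow: one secondary objective, in Phase II subjects implanted with a sponsor device, in South Asia, the only geography to enter Phase II (SAP section 6). The primary objectives, sample size and safety are untouched. It should be corrected because the composites are a tested endpoint and the correction costs almost nothing.

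**What to change.** 1. Check both 6b entries against the administered form and the SF-12 Version 2 scoring manual that the SAP already references (Chapter 8, pages 45-51).
2. Correct the wrong line so that each of the 12 items is scored exactly once.
3. Apply the half-scale missing-item rule to the corrected list.
4. Verify the scoring program with a test record in which all question 6 responses differ, comparing the output with the manual's scoring.

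The cost is one line of SAP text and one test record. Scores already produced can be recalculated if item-level responses are stored. If the program already follows the manual, only the SAP wording changes.
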